6.1 PLAN FOR ORDERLY TERMINATION OF PARTICIPATION

When participants are discontinued from the project by investigator decision, research staff will communicate with the participants to inform participants of the discontinuation, the reason for discontinuation, and offer opportunities for participants to express concerns or ask questions.

When participants are discontinued from the project for any reason (by participant choice or investigator decision), the peer and research staff will do their best to ensure that participants' ongoing needs are met and facilitate referrals as appropriate.

6.2 PARTICIPANT PAYMENT

Participants will be compensated at a rate of approximately \$20 per hour for research activities (i.e., interviews and self-report assessments). This compensation rate is the rate used for similar behavioral health clinical trials at the Syracuse VA and does not appear to lead to undue influence or coercion.

Compensation will occur through established VA payment procedures approved for research activities (e.g., direct deposit or via a VA debit card). Research staff will collect the minimum required identifiable information to properly process their payments (e.g., if research staff need bank account information to complete a direct deposit form, they will collect the necessary information for the form). Veterans will not be compensated for intervention appointments (i.e., Whole Health STEPS appointments with peers). The compensation for each of the study activities is detailed below.

Open Trial Study Activity	Estimated Burden	Compensation
Baseline Part 1 Consent & Eligibility Determination	~ 1 hour	\$20
Baseline Part 2 Remaining Assessments	~ 1 hour	\$20
Post Session Rating Forms (approximately 6 over the study)*	~ ¼ hour each *6 total = ~1.5 hours	\$5 each *6 total = \$30
Mid and Post Treatment Assessment	~1½ hour	\$30
Post Treatment Interview	~ ½ hour	\$10

* To reduce administrative burden with processing multiple payment vouchers for small amounts, the post-session rating forms will be paid in a lump sum at the end of the study along with the post-treatment interview payment unless participants request a different payment schedule.

RCT Study Activity	Estimated Burden	Compensation
Baseline Part 1 Consent & Eligibility Determination	~ 1 hour	\$20
Baseline Part 2 Remaining Assessments	~ 1 hour	\$20
Mid Assessment	~ 1 hour	\$20
Final Assessment	~ 1 hour	\$20
Post Treatment Assessment (added to either Mid or Final Assessment depending on randomization, or administered ASAP after a participant ends peer support services)	~ ½ hour	\$10
Post Treatment Interview	~ ½ hour	\$10

6.3 SAFETY MONITORING PLAN

Following enrollment, participants will be monitored for safety by the peer, clinical staff and research staff. Research staff will review data for safety concerns on an ongoing basis throughout the study. Specifically, when research staff note AEs or SAEs in routine chart reviews or these are reported by participants, staff and/or the peer will document the finding and alert the PI and/or appropriate clinical back-up to ensure that participants have appropriate clinical services and appropriate reporting procedures are initiated.

Suicidality will also be assessed at baseline, mid, and final assessments. Suicidality assessment will consist of the P4 and item 9 of the PHQ-9 at baseline. At follow-up assessments, item 9 of the PHQ-9 will be checked by research study staff immediately after receipt of questionnaires. Positive endorsements of PHQ-9 item 9 will be followed up directly with the Veteran to review original P4 risk assessment, inquire about changes, and re-administer the P4 risk assessment as needed. All Veterans scoring in the

higher risk category on the P4 will be referred to appropriate clinical services (e.g., on call study clinician and/or appropriate VA mental health resources, such as the Emergency Room, available VA mental health provider, Veterans Crisis Line, and/or the Syracuse VA Suicide Prevention Team) and the PI will be notified.

In addition, Veterans will be monitored for safety concerns by the peer during intervention sessions. Peers are trained to recognize potential safety concerns and crises and ensure that the Veteran receives appropriate clinical support (e.g., on call study clinician and/or appropriate VA mental health resources, such as the Emergency Room, available VA mental health provider, Veterans Crisis Line, and/or the Syracuse VA Suicide Prevention Team). The PI will be conducting ongoing supervision of peer support providers and will check-in about potential safety concerns during supervision.

All AEs and SAEs will be reported via established procedures.

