1.2 SCHEMA

2 INTRODUCTION

2.1 STUDY RATIONALE

Functional impairment, limitation in social and occupational roles (Üstün & Kennedy, 2009), is a significant problem for Veterans. Across diagnostic categories, mental health symptoms are associated with functional impairment and difficulty with role-related task (Kazis et al., 1998; Löwe et al., 2008; Spitzer et al., 2006). Despite the availability of services, many Veterans with mental health symptoms do not engage in mental health treatment (Elbogen et al., 2013; Seal et al., 2010). ***Whole Health STEPS (Structured Tiered Engagement with Peer Support) is an innovative approach to engaging this population through combining two novel modalities to engage with Veterans, peer support and Whole Health, tailored for delivery in Primary Care Mental Health Integration (PCMHI) a platform designed to increase access to mental healthcare.***

This two phase pilot trial is designed to address two key objectives (1) evaluate the feasibility and acceptability of Whole Health STEPS and (2) evaluate the preliminary impact of Whole Health STEPS on patient outcomes.

- Phase 1 addresses objective 1 and will be an open trial (Eligible n=10) to test the feasibility of peer delivery in primary care and acceptability to Veterans to inform further manual adjustments. Feasibility of research procedures will also be evaluated to inform adjustments to the research protocol.
- Phase 2 addresses objective 2 and will be a pilot RCT with a waitlist control (Eligible n=44) to evaluate impact on functional impairment and feasibility for subsequent grant applications.

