3 STUDY DESIGN

3.1 OVERALL DESIGN

This study consists of a two phased clinical trial.

Phase 1 is an open trial establishing preliminary feasibility and acceptability of Whole Health STEPS and informing adjustments to the clinical manual. Participants will be followed for the duration of their participation in Whole Health STEPS, a period of approximately 2-3 months. Following phase 1 enrollment, the investigators will review the data, make adjustments to the Whole Health STEPS manual and research protocol as necessary, and proceed with enrollment in Phase 2.

Phase 2 is a 2-arm single-site pilot randomized clinical trial with a waitlist control evaluating Whole Health STEPS impact on patient outcomes and feasibility. Random assignment will be made by research staff following eligibility determination using a stratified permuted block design based on baseline functional impairment (mild-moderate functional impairment $IPF \leq 50$ vs. severe-extreme functional impairment $IPF \geq 51$). Participants will be followed for a period of approximately 4-5 months, 2-3 months will be participation in Whole Health STEPS and 2 months will be either be waitlist or follow-up depending on randomization outcome.

- Hypothesis 2a. Whole Health STEPS will demonstrate an effect size (d) > 0.3 on psychosocial functioning.
- Hypothesis 2b. Whole Health STEPS will demonstrate clinical feasibility including positive results on process outcomes, retention, fidelity, and appropriateness on stepped-care decision points.

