3.3 CONTROL DESCRIPTION: WAITLIST

Veterans randomized to the waitlist control condition will receive Whole Health STEPS after a 2 month wait. During the waitlist period, Veterans will not be prohibited from pursuing any treatment or services they deem appropriate, and healthcare utilization will be tracked through EMR record reviews. Veterans will be provided with information about available emergency and urgent mental health services, resources for social needs (e.g., homelessness), and other important resources to ensure that they are aware of how to engage support as needed.

Waitlist control was selected as the best option for the RCT to evaluate this service package because compared to designs with control groups where only one group receives Whole Health STEPS, it allows a more powerful test of Whole Health STEPS and it provides more feedback data to establish acceptability of the lower intensity interventions which are central to stepped care intervention design.

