6 ASSESSMENT PLAN

Assessments will be conducted with Veterans in person, over the phone, or electronically using Qualtrics or REDCap (Research Electronic Data Capture) depending on format of the assessment, safety guidelines for in person meetings, and Veteran preference. Electronic data collection will be the primary data collection strategy but as a contingency plan if electronic administration is not feasible, staff will make every effort to collect the data in an alternate format (paper or oral format) to reduce data loss. If paper format is used, it will be returned in person or via pre-paid envelope. Research staff will call, text using a VA iPhone and/or send an SMS text via Qualtrics or REDCap, and/or send e-mails via a no-reply, Qualtrics or REDCap generated email address to remind participants to complete assessments as needed. See [Data Security Plan](#) for Qualtrics and REDCap security information. Email and text reminders will follow current VA guidance on information security procedures for these communication methods. If oral format is used, it will be through phone, VA approved video-conferencing format, or in person. As a safety precaution, when conducting assessments virtually, research staff will also confirm a phone number for call back, a physical address for where the Veteran is at that moment, an emergency contact person/phone number in case the Veteran has a medical or mental health emergency while on the phone, and two identifiers to confirm the Veteran's identity.

Electronic medical records data collection will be facilitated by research staff with recruitment activities occurring monthly and outcome data collection occurring at the end of the trial. Upon initial recruitment screening, baseline interviews will be scheduled to review consent and HIPAA information and to determine eligibility. If the Veteran chooses to participate in the study and appropriately answers comprehension questions, research staff will document verbal consent on the approved verbal informed consent script. This modification will reduce burden on participants by eliminating the requirement to travel for a baseline assessment to administer written consent and increase the feasibility of the research trial by broadening the population who will be able to participate.

After obtaining verbal consent, research staff will administer the following assessments at the specified timepoints:

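### Adverse events are not sought in the same way in both arms: peer sessions add a recurring safety contact in one arm at a time, and no general AE question is scheduled for both

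*Combined protocol and SAP*

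**What the plan says.** Section 6.3 (Safety Monitoring Plan) states that "participants will be monitored for safety by the peer, clinical staff and research staff". It provides for continuing review of data by research staff. It also sets out what happens "when research staff note AEs or SAEs in routine chart reviews or these are reported by participants". Suicidality is assessed at baseline, Mid and Final; at the follow-ups this is PHQ-9 item 9, with the P4 repeated as needed. The section then adds a further route: "Veterans will be monitored for safety concerns by the peer during intervention sessions". Supervision of the peers includes a check for safety concerns.

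Section 3.2 says that peer sessions at every level use a semi-structured interview that covers mental health, physical health and social needs. Section 3.3 says: "Veterans randomized to the waitlist control condition will receive Whole Health STEPS after a 2 month wait". Section 3.1 describes the other part of each Veteran's participation: "2 months will be either be waitlist or follow-up depending on randomization outcome".

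Section 6 (Assessment Plan) describes monthly work in the medical record for recruitment, with "outcome data collection occurring at the end of the trial". The schedule table places PHQ-9, GAD-7, PCL-5, AUDIT and self-reported non-VA service use at Mid and Final. No row is a general AE question. UE-ATR, labelled as safety and grouped under STEPS feasibility, shows no timepoint in the text available for review, and section 6.3 does not mention it. Section 11 describes no comparison of AEs between arms.

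**The concern.** The only randomised comparison of STEPS with no STEPS runs from randomisation to Mid. In that window one arm talks regularly to someone who asks about health and needs and is trained to recognise safety concerns. The other arm does not. An AE that is equally common in both arms then has more chances of being recorded under STEPS.

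Two things are at stake. First, raw AE counts by arm would partly measure contact frequency, in a direction that counts against STEPS. The pilot is meant to inform later grant applications and lists safety under feasibility, so even descriptive counts will be read. Second, an event during the wait that is neither suicidality, nor visible on the symptom scales, nor reported as non-VA care may come to light late or not at all. A medical event or a VA admission that the Veteran does not volunteer is an example.

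**Working it through.** The documents give no AE rate, safety sample size or detection rate, so there is no figure of the plan's own to reproduce. Two checks were made.

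**1. Routes by arm, randomisation to Mid**

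| Route | Immediate STEPS | Waitlist |
|---|---|---|
| Peer sessions (3.2, 6.3) | yes, recurring | none during the wait |
| Chart review (6.3) | yes, interval not stated | yes, interval not stated |
| Participant report (6.3) | yes, unprompted | yes, unprompted |
| PHQ-9 item 9, symptom scales, non-VA use (6, 6.3) | at Mid | at Mid |
| General AE question | none scheduled | none scheduled |

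No session count is given for the RCT. The payment table for the open trial (6.2) allows for about 6 post-session forms; taking that as about 6 sessions, scheduled contacts with a safety element before or at Mid are:

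- STEPS: 6 + 1 = about 7
- Waitlist: 0 + 1 = 1

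After Mid the waitlist arm receives STEPS and the immediate arm is in follow-up, so the imbalance reverses.

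Chart review is not fully neutral either. Peer contacts are documented in the medical record (3.2, 7) and peers facilitate referrals (3.2). Before Mid, STEPS charts therefore hold entries that waitlist charts cannot.

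**2. Illustration of unequal detection, true risk ratio 1**

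Let s be the share of events found by the common routes, taken as equal in both arms, and q the share that the peer route would find, taken as independent of the common routes. Both are assumptions.

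- Detection in STEPS = 1 − (1 − s)(1 − q)
- Detection in waitlist = s
- Apparent ratio = [1 − (1 − s)(1 − q)] / s

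| s | q = 0.3 | q = 0.5 | q = 0.8 |
|---|---|---|---|
| 0.9 | 0.93/0.9 = 1.03 | 0.95/0.9 = 1.06 | 0.98/0.9 = 1.09 |
| 0.7 | 0.79/0.7 = 1.13 | 0.85/0.7 = 1.21 | 0.94/0.7 = 1.34 |
| 0.5 | 0.65/0.5 = 1.30 | 0.75/0.5 = 1.50 | 0.90/0.5 = 1.80 |
| 0.3 | 0.51/0.3 = 1.70 | 0.65/0.3 = 2.17 | 0.86/0.3 = 2.87 |

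In events: section 2.1 gives 44 Veterans for the RCT, so 44/2 = 22 per arm if allocation is 1:1 (the ratio is not stated). With an assumed true AE risk of 20% before Mid, each arm has 22 × 0.20 = 4.4 true events. At q = 0.5:

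- s = 0.9: STEPS 4.4 × 0.95 = 4.2, waitlist 4.4 × 0.9 = 4.0
- s = 0.5: STEPS 4.4 × 0.75 = 3.3, waitlist 4.4 × 0.5 = 2.2
- s = 0.3: STEPS 4.4 × 0.65 = 2.9, waitlist 4.4 × 0.3 = 1.3

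The result depends chiefly on s, that is, on how complete and how frequent the chart review is. The protocol does not specify this.

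**The case against.** The strongest reply is that section 6.3 already covers both arms. Continuing review, routine chart review, participant report and the suicidality check apply to everyone. Peer monitoring is introduced as an addition, after the others. The study is described as minimal risk, no AE comparison between arms is planned, and one would be weak anyway: with 22 per arm, power is about 15% for 10% versus 20% and about 30% for 20% versus 40% (two-sided 0.05, assumed).

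Much of this stands, and it rules out four stronger readings that a reader might infer.

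- *AEs are found mainly through peer sessions.* The text does not rank the routes. It supports only that peer sessions are a recurring solicited contact before Mid, in one arm.
- *Chart data arrive only at the end of the trial.* That timing in section 6 is for outcome data. Section 6.3 separately provides for routine chart reviews; only their interval is missing.
- *The one safety instrument has no timepoint.* PHQ-9 item 9 is scheduled at Mid and Final in both arms. The empty UE-ATR cells may be a loss in reading the table, since other rows are empty too.
- *The arms cannot be compared for safety.* Suicidality and symptom worsening are measured at Mid in both arms, so psychiatric deterioration during the wait need not go unseen until after the study.

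The reply does not restore equal detection for other AEs. The common routes are either unprompted or of unstated frequency, and the scheduled questionnaires do not ask about AEs in general. The absence of a planned test does not stop descriptive counts by arm from being biased.

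**Conclusion.** The point holds as a cheap improvement and does not undermine the trial. As written, detection of AEs other than suicidality depends on arm: more contact under STEPS before Mid, and the reverse between Mid and Final. Such events may be under-detected during the 2-month wait, and raw counts could make STEPS look less safe than waiting when it is not.

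The size is not known. With no true difference, the apparent ratio is about 1.0 to 1.1 if the common routes find 90% of events, and about 1.7 to 2.9 if they find 30%. With 22 per arm and a 20% true risk, this is a difference of a fraction of an event up to one or two events at q = 0.5. These figures rest on assumed detection rates, independent routes, 1:1 allocation and an assumed AE risk. They show direction and range and are not an estimate.

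**What to change.** - Add one structured AE/SAE question, worded identically in both arms and asking about the time since the last assessment, to the Mid and Final assessments.
- State when the safety chart review of section 6.3 is done, and do it at the same points (Mid and Final) in both arms. Make clear in section 6 that the end-of-trial timing concerns outcome data only.
- Report AEs descriptively by arm, period (randomisation to Mid, Mid to Final) and source. Base the comparison between arms on the common sources, and list peer-detected events and peer-authored chart notes separately.
- Check the UE-ATR row against the original table. If it is blank there too, give it a timepoint and mention it in section 6.3.

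The cost is a few more minutes at two assessments that are already scheduled, chart reviews at fixed points by staff who already work in the record monthly for recruitment, and more minor events to process.

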7 RESEARCH STUDY DOCUMENTATION PLAN

CPRS documentation will include documentation of research study initiation, research study completion, and relevant clinical tasks. Routine research study activities (e.g., completing self-report assessments) which are expected during the course of the study but do not inform the Veteran's healthcare will be described in the research study initiation note but not documented separately. Peer services will be documented in clinically appropriate progress notes in a manner consistent with usual clinical practice and peers' role as either clinical or research staff. Additional documentation will be entered into CPRS as needed and appropriate to ensure Veteran continuity of care (e.g., referrals for services, information regarding suicide risk, etc.).

8 RISK AND BENEFITS

The potential benefits of the project outweigh the minimal risks.

8.1 RISKS

There is minimal risk from participation in any of the research activities. The procedures are non-invasive and will not cause physical harm to participants. There are no known risks associated with peer services or the Whole Health model; both are part of standard care offered through the VA. There is minimal psychological risk (i.e., embarrassment, discomfort) to participants when asked to share sensitive information about themselves (e.g., suicidal thoughts, mental health symptoms) with research staff or the peer. No deception is involved in this study.

8.2 MINIMIZING RISKS

Participants will be assessed for suicide risk according to an established protocol and directly referred for additional services (e.g., Veterans' Crisis Line, VA Emergency Room, VA mental health provider, Suicide Prevention Team) as appropriate if they are at high risk. Research assistants will be trained to provide grounding/relaxation activities as appropriate to participants who experience mild psychological discomfort (e.g., distress, frustration, anxiety) as a result of any study activities. Further, any Veteran can be connected with an on-call clinician or mental health provider at any point in the study at their request or if they report mental health symptoms which are concerning to the peer or research staff. Also, facilitating engagement with services, including mental health treatment as needed, is part of the

Whole Health STEPS approach. To minimize risk of breaching confidentiality, all electronic and paper self-report data collected will be identified by a random identification number rather than individually identifiable information. Identifiable information including voice recordings, informed consent, payment status, and enrollment information will be stored separately and in accordance with the data security and privacy procedures. Data security and privacy procedures are designed to minimize this risk.

8.3 BENEFITS

The study has multiple potential direct and indirect benefits to participants. One potential direct benefit is that interviews, telephone screenings, and assessment sessions may provide the opportunity for participants to thoughtfully reflect on their current situation and which may increase insight and prompt change (e.g., behavior change or seeking additional treatment). Additionally, all Veterans will receive Whole Health STEPS which may be beneficial given past research on peer support and Whole Health services. Indirect benefits include the opportunity to learn about and participate in clinical research that aims to improve Veteran healthcare. The data and feedback collected in this project will serve to improve services offered for all Veterans.

9 DATA SECURITY PLAN

The PI will oversee data and safety monitoring to ensure safety of participants and integrity of data collected. All research staff and the peer will have training appropriate to their roles in data management and security.

The VA Informatics and Computing Infrastructure (VINCI) will be used to facilitate EMR data collection. VINCI is a Department of Veterans Affairs (VA) Health Services Research & Development (HSR&D) resource center that provides a secure, central analytic platform for performing research and supporting clinical operations activities. It is a partnership between the VA Office of Information Technology (OI&T) and the Veterans Health Administration Office of Research and Development (VHA ORD). VINCI includes a cluster of servers for securely hosting suites of databases integrated from select national VA data sources. VINCI servers for data, applications and virtual sessions are physically located at the VA Austin Information Technology Center (AIRC), located in Austin, Texas. This secure enclave with 105 high-performance servers and 1.5 petabytes of high-speed data storage has multiple layers of security and disaster recovery to prevent data loss.

Coded self-report survey data will be collected using Qualtrics or REDCap, web-based data collection tool. Paper/Pen and oral administration (documented in Qualtrics, REDCap, or Paper/Pen) will be used as contingency plans. Participants will be invited to supply an email address during the baseline interview which will be used to generate a reminder email from Qualtrics or REDCap containing a link to complete follow-up assessments. This email will come from a no-reply, Qualtrics or REDCap generated email address. Participants can choose not to supply an email address. Participants who prefer to receive a text message link of Qualtrics or REDCap surveys will be texted via the phone number that is stored in the Access log. In instances where Qualtrics or REDCap are used, participants will complete online surveys via Qualtrics or REDCap, but VA research staff will download and store all data in one database which will be built and will reside on a VA secured network drive. Qualtrics is hosted in a FedRAMP authorized environment and is compliant with VA security policy (See Qualtrics Security Statement, <https://www.qualtrics.com/security-statement/>). REDCap is hosted on the VA Enterprise Cloud (VAEC) and was developed specifically around HIPAA-Security guidelines.

All data from this study will be stored in locked filing cabinets and password-protected secure computer networks at the Syracuse VA. Only approved research staff and relevant oversight committees will have access to the data. All data will be kept strictly confidential and secure per VA policies, American Psychological Association (APA) ethical standards, and human subjects research policies. Identifiable data will be stored separate from de-identified data in locked filing cabinets and password protected computer files on a VA secured network drive.

Study records will be retained in accordance with current VA policies (VHA Records Control Schedule). Identifiers will be maintained through the duration of the research study and then destroyed consistent with VA policy.

